11.1. Data Capture System

An EDC system will be used in this study. The site maintains a separate source for the data entered by the site into the sponsor-provided EDC system.

Some or all of a subject's data will be directly entered into the eCRF at the time that the information is obtained. In instances where the data cannot be directly data entered, the site will maintain source documentation in the trial files and the subject's data will be transcribed into the eCRF. Any data for which the eCRF will serve as the source document, or any other data not entered directly into the eCRF (for example, ePRO interactive voice response system [IVRS] or patient rated outcomes), will be identified and documented by site in the site's trial file. For data handled by a data management third party organization (TPO), eCRF data and some or all data that are related will be managed and stored electronically in the TPO system. Subsequent to the final database lock, validated data will be transferred to the sponsor.

For data handled internally, eCRF data and some or all data that are related will be managed by the sponsor and stored electronically in the sponsor's system.

In this study, patient cluster headache data will be collected directly via an ePRO diary as part of an ePRO/Clinical Outcome Assessment (COA) system. In addition, the patient-rated PGI-I; clinician-rated C-SSRS, SHSF and SHFU are collected at office visits as part of the ePRO/COA system .

If ePRO/COA records are stored at a third party site, investigator sites will have continuous access to the source documents during the study and will receive an archival copy at the end of the study for retention.

Any data for which the ePRO/COA instrument record will serve to collect source data will be identified and documented by each site in that site's study file.

Case report form data collected by the TPO will be encoded by the TPO and stored electronically in the TPO's database system. Validated data will subsequently be transferred to the sponsor using standard Lilly file transfer processes.

Data managed by a central vendor, such as laboratory test data, will be stored electronically in the central vendor's database system. Data will subsequently be transferred from the central vendor to the Lilly generic labs system. Data from complaint forms submitted to Lilly will be encoded and stored in the global product complaint management system.

12. Sample Size and Statistical Methods

12.1. Determination of Sample Size

The study is planned to have a minimum of approximately 162 patients randomized 1:1 to placebo or LY2951742 with the opportunity to increase the final sample size at an interim analysis if indicated in order to maintain a well powered study. To preserve blinding, details of the sample size and power calculations are omitted from this protocol and are provided in a separate document to the ERB.

12.2. Statistical and Analytical Plans

12.2.1. General Considerations

Unless otherwise specified, efficacy analyses will be conducted on an ITT population, which include all patients who are randomized and receive at least 1 dose of IP. Patients in the ITT population will be analyzed according to the treatment group to which they were randomized. Safety analyses for SP III and exposure will be conducted on the safety population, which also includes all patients who are randomized and receive at least 1 dose of study drug. However, patients will be analyzed by actual study treatment received most often (modal treatment; placebo or LY2951742) during the double-blind treatment phase. Safety analyses during LY2951742-treated time and LY2951742-treated time plus post-treatment time will be conducted on the LY2951742-treated population, which includes all patients who receive at least 1 dose of LY2951742. When mean change from baseline is assessed, the patient will be included in the analysis only if he/she has a baseline and a post-baseline measurement. Additional analyses population for analyses of study Phase IV and Phase V will be described in the SAP.

Baseline will be the last 14 days in the eligibility report (pre-randomization diary phase). An additional baseline defined at Visit 9 (the first visit of the open-label phase) may be used for some analyses. This, in addition to details for handling missing data, will be further outlined in the SAP.

Treatment effects will be evaluated based on a 2-sided significance level of 0.05 for all the efficacy and safety analyses. The 95% CIs for the difference in least-square means (LSMeans) between treatment groups will be presented. Adjustments for multiple comparisons for the analyses corresponding to the primary and gated secondary objectives are described in the sections on the primary and secondary efficacy analyses below. There will be no adjustments for multiplicity for analyses of other data.

Any change to the data analysis methods described in the protocol will require an amendment ONLY if it changes a principal feature of the protocol. Any other change to the data analysis methods described in the protocol, and the justification for making the change, will be described in the clinical study report.

Additional exploratory analyses of the data will be conducted as deemed appropriate.

Statistical analysis of this study will be the responsibility of Lilly or its designee. SAS® software will be used to perform most or all statistical analyses.

12.2.2. Patient Disposition

All patients who discontinue from the study will be identified, and the extent of their participation in the study will be reported. If known, a reason for their discontinuation will be given.

The number and percentage of ITT patients who complete the study or discontinue early will be tabulated for both treatment groups for SP III, SP IV, and SP V both overall and by visit.

Reasons for discontinuation will be compared between treatment groups for SP III using Fisher's exact test. Descriptive statistics only will be presented for the treatment groups in SP IV and SP V.

12.2.3. Patient Characteristics

The following patient characteristics will be recorded at baseline and will be summarized by treatment groups for all ITT patients:

- Demographic (age, gender, race, ethnicity, country, region, height, weight, BMI)
- Baseline disease characteristics, such as:
 - number of weekly cluster headache attacks
 - number of times an abortive medication was taken
 - average severity of cluster headache pain
 - average cluster headache attack duration
 - number of times an abortive medication was taken per cluster headache attack
- Baseline alcohol, tobacco, caffeine and nicotine consumption
- Medical history and pre-existing condition
- Prior cluster headache history in last 7 days prior to Visit 1

Comparisons between treatment groups will be performed using Fisher's exact tests for categorical data and analysis of variance (ANOVA) with treatment and pooled investigative sites as independent variables in the model for continuous data.

Medical history and pre-existing conditions will be summarized by preferred term (PT) within system organ class (SOC), and comparison between treatment groups will be performed using Fisher's exact test.

12.2.4. Concomitant Therapy

The proportion of patients who received concomitant medication (including preventive medication) and abortive medications for cluster headache attacks will be summarized separately

for all ITT patients for SP III, SP IV and SP V. Treatment group comparisons will be done using Fisher's exact test for SP III with ITT population. Descriptive statistics only will be presented for the treatment groups in SP IV and SP V.

12.2.5. Treatment Compliance

Treatment compliance will be calculated for SP III and SP IV as:

$$\frac{\text{number of full doses received} * 100}{\text{number of intended full doses}}$$

Comparisons between treatments for treatment compliance will be performed using an ANOVA with treatment and pooled investigative site in the model.

12.2.6. ePRO Diary Compliance

The ePRO diary compliance at each biweekly interval (including baseline, Weeks 1/2, 3/4, 5/6, 7/8, 9/10, 11/12, 13/14, and 15/16) and for SP III (Weeks 1/2 through 11/12) will be calculated. Diary compliance at each interval is calculated as:

$$\frac{\text{Actual number of diary entry days in the interval} * 100}{\text{Expected number of diary entry days in the interval}}$$

The diary entry can only be saved and submitted after all the required ePRO questions are answered, so the actual number of diary entry days represents the total number of days with non-missing answer to all the required cluster headache attack ePRO questions. The expected number of diary entry days will be calculated as (the last calendar date - the first calendar date in each interval +1).

Comparisons between diary compliance for each interval separately will be performed using an ANOVA with treatment and pooled investigative site in the model.

Compliance will also be listed by biweekly interval for each patient.

12.2.7. Primary and Gated Outcome and Methodology

12.2.7.1. Primary Outcome

The primary analysis will be conducted by a REML-based, MMRM analysis using all the longitudinal observations at Weeks 1/2, 3/4, 5/6, 7/8, 9/10, and 11/12 intervals. The analysis of the primary outcome will be the main effect of treatment between LY2951742 300 mg and placebo during the 12-week double-blind treatment phase from a repeated measures analysis on mean change from baseline in the weekly attack frequency. This provides the average treatment effect across the 12-week double-blind treatment phase.

The model for the primary analysis will include the fixed, categorical effects of treatment, gender, verapamil use, pooled investigative site, week, and treatment-by-week interaction, as well as the continuous, fixed covariates of baseline value. An unstructured covariance structure will be used to model the within-patient errors. The Kenward-Roger (Kenward and Roger 1997)

approximation will be used to estimate denominator degrees of freedom. If the model does not converge with both the Hessian and the G matrix being positive definite under the default fitting algorithm used by PROC MIXED, the Fisher's scoring algorithm will be implemented by specifying the SCORING option in SAS®. If the model still fails to converge, the model will be fit using covariance matrices of the following order specified by a decreasing number of covariance parameters until convergence is met:

- Heterogeneous Toeplitz
- Heterogeneous First-order autoregressive
- Toeplitz
- First-order autoregressive

If necessary, both the default and the scoring fitting algorithms will be used in the prespecified order before proceeding to the next covariance structure in the sequence. For models where the unstructured covariance matrix is not utilized, the sandwich estimator (Diggle and Kenward 1994) will be used to estimate the standard errors of the fixed effects parameters. The sandwich estimator is implemented by specifying the EMPIRICAL option in SAS®. When the sandwich estimator is utilized, the Kenward-Roger approximation for denominator degrees of freedom cannot be used. Instead, the denominator degrees of freedom will be partitioned into between-subject and within-subject portions by the DDFM=BETWITHIN option in SAS®.

If the sample size is increased as a result of the interim analysis, the CHW procedure (Cui et al. 1999) will be applied to the primary endpoint to control the type I error at a one sided $\alpha=0.025$ significance level. The CHW method ensures strong control of type 1 error when the sample size is increased in a data dependent manner.

If the sample size is increased as a result of the interim analysis, an unadjusted point estimate for the primary efficacy analysis will be calculated and reported. A median unbiased point estimate and a stage-wise adjusted confidence interval for the primary efficacy analysis will be calculated and reported based on the approach described in Brannath et al. (2009) to assess sensitivity of the point estimate.

12.2.7.2. Gated Secondary Outcomes

For the gated secondary outcome of the estimated mean proportion of patients with a 50% or greater reduction from baseline in weekly cluster headache attack frequency during the 12-week double-blind treatment phase, a categorical, pseudo-likelihood-based repeated measures analysis of data at Weeks 1/2, 3/4, 5/6, 7/8, 9/10, and 11/12 will be used. The endpoint for comparing LY2951742 with placebo will be estimated as the main effect of treatment from the categorical MMRM analysis across Weeks 1 to 12. This analysis will be implemented using the GLIMMIX procedure in SAS® to compare treatments and include the fixed, categorical effects of treatment, gender, verapamil use, visit/week, and treatment-by-visit/week interaction, as well as the continuous, fixed covariate of baseline value.

For the gated secondary outcome of sustained response (the proportion of patients with a reduction from baseline of 50% or greater in the weekly cluster attack frequency beginning at

Weeks 3/4 and maintained at Weeks 5/6, 7/8, 9/10, and 11/12), the Koch's Nonparametric Randomization-Based Analysis of Covariance method will be utilized (Koch et al. 1998). A non-responder imputation for missing values will be used. Specifically, all patients who discontinue study treatment at any time prior to Weeks 11/12, for any reason, will be considered a non-responder at all missing assessment.

If the sample size is increased, the CHW test statistic will be calculated for the gated secondary objectives. The analysis of the secondary gatekeeper objectives will be performed if the LY2951742 versus placebo comparison is significant for the primary efficacy analysis at a one sided $\alpha=0.025$ significance level.

12.2.8. Efficacy Analyses

The secondary and exploratory efficacy analyses will be conducted for SP III and SP IV.

For the continuous secondary and exploratory efficacy measures, the change from baseline to each 2 week interval post-baseline measure will be analyzed from repeated measures analyses. For the efficacy measures that are not derived from cluster headache attack frequency, the baseline average daily cluster headache attack frequency category (≤ 4 vs. > 4) will be added as a covariate in the MMRM model.

For the categorical secondary and exploratory efficacy measures including 30% response, 50% response, 75% response and 100% response, the percentage of patients meeting response criteria at each biweekly interval will be estimated for each treatment from a categorical, pseudo-likelihood-based repeated measures analysis of longitudinal binary outcomes indicating whether patients meet response criteria. This analysis will be implemented using the GLIMMIX procedure in SAS®.

CCI

CCI

[REDACTED]

[REDACTED]

12.2.10. Safety Analyses

The safety analyses will be conducted for SP III on the safety population, and during LY2951742-treated time and LY2951742-treated time plus post-treatment time on the LY2951742-treated population.

The safety and tolerability of treatment will be assessed by summarizing the following:

- Adverse events
 - TEAEs

- by PT
- by SOC
- by maximum severity
- considered to be related to IP by investigator
 - serious adverse events
 - adverse events leading to discontinuation
- Suicidal ideation and behaviors assessed by solicited questioning using the C-SSRS
- Vital signs and weight
- Electrocardiograms
- Laboratory measurements
- Anti-drug antibodies (ADA and NAb)

12.2.10.1. Categorical Safety Variables

Unless specified otherwise, the categorical safety analyses will include both scheduled and unscheduled visits.

Comparisons between treatment groups for all categorical safety measures will be made using Fisher's exact test for SP III with safety population. Descriptive statistics only will be presented for the analyses with LY2951742-treated population.

12.2.10.2. Adverse Events

Treatment-emergent adverse events are defined as the reported AEs that first occurred or worsened during the post-baseline phase compared with baseline phase. For each TEAE, the severity level of the event (mild, moderate, or severe) will be determined by patient or physician opinion. The Medical Dictionary for Regulatory Activities (MedDRA) Lowest Level Term (LLT) will be used in the treatment-emergent computation. For each LLT, the maximum severity at baseline will be used as the baseline severity. If the maximum severity during post-baseline is greater than the maximum baseline severity, the event is considered to be treatment-emergent for the specific post-baseline period. For each patient and TEAE, the maximum severity for the MedDRA level being displayed (PT, High Level Term (HLT), or SOC) is the maximum post-baseline severity observed from all associated LLTs mapping to that MedDRA level.

For events that are gender-specific, the denominator and computation of the percentage will include only patients from the given gender.

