10.2.1. Adverse Events

Lilly has standards for reporting AEs that are to be followed regardless of applicable regulatory requirements that may be less stringent.

Lack of drug effect is not an AE in clinical studies, because the purpose of the clinical study is to establish drug effect.

Cases of pregnancy that occur during maternal or paternal exposures to IP should be reported. Data on fetal outcome and breast-feeding are collected for regulatory reporting and drug safety evaluation.

Study site personnel will record the occurrence and nature of each patient's pre-existing conditions, including clinically significant signs and symptoms of the disease under treatment in the study.

After the ICF is signed, site personnel will record any change in the condition(s) and the occurrence and nature of any AEs. All AEs related to protocol procedures are reported to Lilly or designee via electronic case report form (eCRF) into the Lilly designated electronic data capture system (EDC).

In addition, all AEs occurring after the patient receives the first dose of IP must be reported to Lilly or its designee via eCRF.

Any clinically significant findings from ECGs, laboratory measurements, vital sign measurements, other procedures, and so on that result in a diagnosis should be reported to Lilly or its designee using eCRF.

Investigators will be instructed to report to Lilly or its designee their assessment of the potential relatedness of each AE to protocol procedure, cluster headache, IP, using eCRF.

The investigator decides whether he or she interprets the observed AEs as either related to disease, to the study medication, study procedure, or other concomitant treatment or pathologies. To assess the relationship of the AE to the IP, the following terminologies are defined:

- **Related:** a direct cause and effect relationship between the study treatment and the AE is likely.
- **Possibly related:** a cause and effect relationship between the study treatment and the AE has not been demonstrated at this time and is not probable, but is also not impossible.
- **Unrelated:** without question, the AE is definitely not associated with the study treatment.

For analytical purposes only, according to Lilly's standard operating procedures all "related" and "possibly related" AEs and SAEs will be defined as related to the IP.

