5.5.4. Patient Characteristics

The following patient characteristics at baseline will be summarized by treatment group for all ITT patients.

- demographic (age, gender, race, ethnicity, country, region, height, weight, body mass index)
- baseline disease characteristics:
 - number of weekly cluster headache attacks
 - average severity of cluster headache pain for the cluster headache attack days
 - weekly total cluster headache attack duration
 - weekly number of times of using oxygen
 - weekly number of times of using oral triptan, sumatriptan nasal spray, or zolmitriptan nasal spray
 - weekly number of times of using sumatriptan Sc
 - weekly number of times of using acetaminophen/paracetamol or NSAIDs
 - number of times of using oxygen per cluster headache attack

- number of times of using oral triptan, sumatriptan nasal spray, or zolmitriptan nasal spray per cluster headache attack
- number of times of using sumatriptan Sc per cluster headache attack
- number of times of using acetaminophen/ paracetamol or NSAIDs per cluster headache attack
- total weekly dose for oral triptan, sumatriptan nasal spray, and zolmitriptan nasal spray combined
- total weekly dose for sumatriptan Sc
- total weekly dose for oral triptan
- total weekly dose for sumatriptan nasal spray
- total weekly dose for zolmitriptan nasal spray
- prior cluster headache history in last 7 days prior to Visit 1
- baseline alcohol, tobacco, caffeine, and nicotine consumption
- medical history and pre-existing conditions

Comparisons between treatment groups will be performed using Fisher's exact test for categorical data and analysis of variance (ANOVA) with treatment and pooled investigative site as independent variables in the model for continuous data.

Medical history and pre-existing conditions will be summarized by descending frequency of Preferred Term (PT) within System Organ Class (SOC) and by descending frequency of PT respectively, and comparison between treatment groups will be performed using Fisher's exact test. Medical history is defined as illness(es) that ended prior to the signing of informed consent. Pre-existing conditions are medical events ongoing at the time of informed consent.

5.5.5. *Exposure to Investigational Product*

Patients will receive the investigational product (IP) at Month 0, 1, 2, 3, ..., up to Month 14.

The following information will be recorded on the electronic case report form (eCRF) for each dose:

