5.5.9.1.1. Adverse Events

Treatment-emergent AEs are defined as the reported AEs that first occurred or worsened during the post-baseline phase compared with baseline phase. For events occurring on the day of first administration of study drug and on the day of first open-label treatment when applicable, the CRF-collected flag will be used to determine whether the event was pre-treatment versus post-

treatment. For each TEAE, the severity level of the event (mild, moderate, or severe) will be determined by patient or physician opinion. The Medical Dictionary for Regulatory Activities (MedDRA) Lowest Level Term (LLT) will be used in the treatment-emergent computation. For each LLT, the maximum severity at baseline will be used as the baseline severity. If the maximum severity during post-baseline is greater than the maximum baseline severity, the event is considered to be treatment-emergent for the specific post-baseline period. For events with a missing severity during the baseline period, it will be treated as “mild” in severity; for events with a missing severity during the postbaseline period it will be treated as “severe” for TEAE computation. For each patient and TEAE, the maximum severity for the MedDRA level being displayed (PT, High-Level Term [HLT], or SOC) is the maximum postbaseline severity observed from all associated LLTs mapping to that MedDRA level.

For events that are gender-specific, the denominator and computation of the percentage will include only patients from the given gender.

5.5.9.1.1.1. Potential Hypersensitivity Events

Potential hypersensitivity events will be defined using the following terms (standard MedDRA query [SMQ]):

- broad and narrow terms in the Anaphylactic reaction SMQ (20000021)
- broad and narrow terms in the Angioedema SMQ (20000024)
- broad and narrow terms in the Hypersensitivity SMQ (20000214)

A listing of patients having an event identified from these analyses will be medically reviewed to determine if the terms identified represent events likely hypersensitivity in nature. Listings should include information on timing of event relative to latest dose of study drug administration, the event term from this query, other AEs for the patient and timing, any abnormal laboratory findings, concomitant medication, medical history and pre-existing conditions. Only those that are judged medically to be events likely hypersensitivity in nature will be included in the final tables.

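### The rule for the displayed severity of a treatment-emergent adverse event is not limited to the LLTs that are themselves treatment-emergent, so read literally a milder new event can be shown at the severity of an older one

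*Protocol*

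**What the plan says.** Protocol 12.2.10.2 sets the unit for the emergence test: "The Medical Dictionary for Regulatory Activities (MedDRA) Lowest Level Term (LLT) will be used in the treatment-emergent computation". Baseline is also taken term by term: "For each LLT, the maximum severity at baseline will be used as the baseline severity". The test is then: "If the maximum severity during post-baseline is greater than the maximum baseline severity, the event is considered to be treatment-emergent".

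The next sentence moves up the hierarchy. It opens "For each patient and TEAE, the maximum severity for the MedDRA level being displayed (PT, High Level Term (HLT), or SOC", and it defines the displayed severity as the one that "is the maximum post-baseline severity observed from all associated LLTs mapping to that MedDRA level".

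SAP 5.5.9.1.1 keeps the same two steps and the same source for the displayed severity: "is the maximum postbaseline severity observed from all associated LLTs mapping to that MedDRA level". SAP 5.5.9.1.1.2 (injection sites) and 5.5.9.1.1.3 (upper respiratory tract infections) repeat the rule at PT level. SAP 5.5.9.1.1.1 plans a severity table for likely hypersensitivity events, also by PT, without a rule of its own, so the general rule would apply there. No section limits the maximum to LLTs that met the emergence test.

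**The concern.** Two units are in use. Emergence is a property of an LLT, while displayed severity is a property of a PT, HLT or SOC and draws on every LLT beneath it. An LLT that failed the emergence test, because it was already present at the same or greater severity, can therefore supply the severity shown for a different LLT that passed.

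TEAEs by maximum severity is a planned summary in protocol 12.2.10 and SAP 5.5.9, and categorical safety measures are compared between arms in SP III by Fisher's exact test. The rule is the same in both arms, but it acts only on patients who have a TEAE under the heading. The arm with more mild TEAEs therefore gains more entries in the severe row, and an absolute difference in mild events can appear as a difference in severe ones.

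**Working it through.** The plan gives no figure on this point, so there is none to reproduce. The check applies the written rule and then shows a range under stated assumptions.

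**Step 1: one patient.** Code severity as 0 none, 1 mild, 2 moderate, 3 severe, and write each LLT as (baseline, post-baseline). An LLT is emergent if the second number exceeds the first. Put two LLTs under the same displayed heading:

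- A = (3, 3): not emergent.
- B = (0, 1): emergent and mild.

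Maximum over all LLTs = max(3, 1) = 3, shown as severe. Maximum over emergent LLTs only = 1, shown as mild.

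**Step 2: when the two readings differ.** With one LLT under the heading there are 6 emergent patterns and none differ, because the emergent LLT supplies its own maximum. With two LLTs there are 16 × 16 = 256 ordered patterns. Each LLT has 10 non-emergent patterns, so 256 − 10 × 10 = 156 contain at least one emergent LLT. The displayed severity exceeds that of every emergent LLT in 10 of these. In 2 of the 10 (the pair above, in either order) a mild event becomes severe. These count logical possibilities; they are not rates.

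**Step 3: whether non-emergent LLTs can be in the post-baseline data.** The emergence test compares an LLT's post-baseline severity with its own baseline, so it presupposes LLTs observed in both periods. An event that continues or recurs at its baseline severity fails the test but has a post-baseline severity. SAP Table CGAM.5.3 adds a second route. In the GMB-treated analyses, the TEAE baseline for patients who had placebo in SP III runs from Visit 1 to Visit 9 before open-label dosing. Their graded SP III events thus become baseline, and one that persists unchanged is non-emergent.

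**Step 4: size under assumptions.** All inputs are assumed:

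- TEAE rate under one heading: 10% on drug, 6% on placebo.
- 5% of those TEAEs are truly severe.
- A share s of patients, equal in both arms and independent of the TEAE's own severity, has an unchanged severe non-emergent LLT under that heading.

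Severe incidence as written = TEAE rate × (0.05 + 0.95 × s).

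| s | Factor | Drug | Placebo | Difference (points) |
|---|---|---|---|---|
| 0% | 0.05 | 0.50% | 0.30% | 0.20 |
| 5% | 0.0975 | 0.975% | 0.585% | 0.39 |
| 20% | 0.24 | 2.40% | 1.44% | 0.96 |
| 80% | 0.81 | 8.10% | 4.86% | 3.24 |

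The ratio between arms stays at 10/6 in every row. The level and the absolute difference are what grow, by a factor of 0.0975/0.05 = 1.95 when s is 5%.

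**The case against.** The best defence is that the sentence begins by referring to each patient and TEAE, so the associated LLTs are only those that make up the treatment-emergent event. That reading is possible and may be what was intended. But the only explanation the text gives of which LLTs are associated is that they map to the displayed level, and the restriction is written nowhere. Two programmers could build different tables from it.

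Other parts of the defence stand:

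- The general lists of safety summaries do not name the MedDRA level of the severity table. Where the SAP names a level for a severity table, it is PT, and there the problem needs two LLTs under one PT and is rare.
- For injection-site events in SP III, baseline precedes the first study injection, so a study-related injection-site LLT cannot already be present. The exposure there is essentially the GMB-treated analysis of patients who first had placebo injections, and that analysis is descriptive only.

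A reader might infer that nearly every patient carries a severe baseline term, since the diagnosis requires severe or very severe pain (protocol 8.1.1) and sites record "pre-existing conditions, including clinically significant signs and symptoms of the disease under treatment in the study". The documents do not support this. Section 8.1.1 describes attack pain for diagnosis and is not a grade on the adverse-event scale. Attack pain during the trial goes into the diary on a separate 0 to 4 scale (protocol 10.1.1). Recording a condition as pre-existing does not grade it severe. Nor do the documents say which SOC cluster headache shares with other events. The 80% row is therefore an extreme of the range, and a share near 0%, where the effect vanishes, is equally consistent with the text.

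**Conclusion.** The point holds as a defect of the written rule. Taken literally, it can show a new, milder TEAE at the severity of a non-emergent LLT under the same heading, and no other section prevents this. It would be too strong to say that the tables will misreport mild events as severe. That depends on how the sentence is programmed and on how many patients have two such LLTs under one heading, and the documents settle neither.

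The assumed rates put the severe-event difference between 0.2 points (share 0%) and 3.2 points (share 80%), with 0.4 points at a share of 5%. These figures rest wholly on the assumed 10%, 6% and 5% and on the chosen share. Only the maximum-severity summaries are touched; TEAE incidence, SAEs, discontinuations and efficacy are not. The correction is worth making because it is specific and nearly free.

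**What to change.** Insert the word treatment-emergent before LLTs in the severity sentence of protocol 12.2.10.2 and SAP 5.5.9.1.1, 5.5.9.1.1.2 and 5.5.9.1.1.3, so that the maximum runs only over LLTs that are themselves emergent for the analysis period and map to the displayed level. Filter the severity tables, including the hypersensitivity table, on the existing treatment-emergent flag.

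The cost is one word in four places and one filter in the table program. No new data are needed. Protocol 12.2.1 and SAP 5.5.1 require an amendment only when a principal feature of the protocol changes. This clarification does not appear to be one, so it can be made in the SAP and explained in the clinical study report.
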